### **2.3.5      Safety Endpoints**

Safety parameters to be measured include exposure, adverse events (including serious adverse events, adverse events of special interest, adverse events leading to drug discontinuation, and deaths), clinical laboratory results (hematology, chemistry, anti-FVIII and anti-emicizumab antibodies), vital signs, ECG, and concomitant medication use.

### **2.3.6      Exploratory Biomarker Endpoints**

Exploratory biomarker endpoints include

- Pharmacodynamic (PD) biomarkers of emicizumab, including but not limited to aPTT, thrombin generation, and FVIII activity

## **2.4            DETERMINATION OF SAMPLE SIZE**

The sample size for this study is based on clinical rather than statistical considerations, taking into account the limited number of patients with hemophilia A available for

participation in clinical studies and in an effort to collect sufficient data to assess the safety and efficacy of emicizumab.

The sample size calculation is based on the evaluation of the primary efficacy endpoint, defined as the number of bleeds over time (i.e., bleed rate) with emicizumab (treatment group,  $\lambda_t$ ) versus no prophylaxis (control group,  $\lambda_c$ ), which are said to follow a negative binomial (NB) distribution. With consideration of enrollment feasibility, a sample size of 70 patients, assuming an allocation ratio of 2:2:1 (28 patients in each randomized treatment group and 14 patients in control group), will achieve a power of more than 90% assuming a mean ABR of 4 and 18 bleeds (with variances=mean  $\times$  10) for the emicizumab treatment and control arms respectively, representing an expected 78% reduction in the ABR compared to the control arm. Initial sample size calculations were performed with East®, Version 6 (Cytel, Cambridge, MA), assuming the patients from each treatment group are followed up to 0.5 units of time (i.e., 24 weeks).

However, the above approach to sample size calculation assumes similar follow-up for each patient. Because this is unlikely to be seen in the study, power was also estimated by simulation to account for different follow-up times among patients. Conducting simulations on the basis of an NB regression model including an offset variable to account for variable follow-up times, with all other assumptions remaining the same as previously described, the sample size is projected to have greater than 90% power at the 2-sided 0.05 level of significance.

## **2.5 ANALYSIS TIMING**

The primary efficacy analysis to assess the effect of emicizumab on bleed rate reduction will be performed at the earliest timepoint when all randomized patients (Arms A, B, and C) have either completed 24 weeks of study treatment or discontinued from the study.

The final analysis will occur at the end of the study, as defined in the protocol. No interim analysis is planned for the study.

## **3. STUDY CONDUCT**

### **3.1 RANDOMIZATION ISSUES**

Patients who received episodic treatment with FVIII or bypassing agents prior to study entry will be randomized in a 2:2:1 ratio to receive either emicizumab prophylaxis at 3 mg/kg/wk subcutaneously for 4 weeks, followed by 1.5 mg/kg/wk (Arm A) or 6 mg/kg/4wks (Arm B) subcutaneously, or to the control arm (no prophylaxis; Arm C). A central randomization procedure will be used for all patients who fulfill the entry criteria at screening. A block based randomization method will be used, stratified by the number of bleeds in the last 24 weeks (<9 or  $\geq$ 9). The proposed randomization method is designed to balance treatment group assignment within the prognostic stratification factor.

## 4. **STATISTICAL METHODS**

### 4.1 **OUTPUT LAYOUTS**

The key output layouts are designed to address the study objectives in a flexible manner and provide an overall view of the efficacy and safety of emicizumab. In particular, patients in Arm C are allowed to switch to receive emicizumab after the first 24 weeks in the study, yielding two “study periods” (i.e., when they receive no prophylaxis for the first 24 weeks [no prophylaxis period, designated Arm Ccontrol] and emicizumab prophylaxis thereafter [emicizumab period, designated Arm Cemi]). These two periods are analyzed separately, and either period can be displayed on outputs together with the other treatment arms.

The three key output layouts are:

- **Randomized patients:** comparison of either emicizumab 1.5 mg/kg/wk (Arm A) versus no prophylaxis (control arm [Arm Ccontrol]) prior to switch to emicizumab) or emicizumab 6 mg/kg/4wks (Arm B) versus no prophylaxis (Arm Ccontrol), within a single output produced for all comparisons involving arms A, B, and C prior to switch (Arm A versus Arm Ccontrol and Arm B versus Arm Ccontrol); these outputs form the core set of the efficacy comparisons and will be supported by a corresponding safety analysis. Randomized patients will be used to describe the baseline characteristics and study conduct
- **All emicizumab patients:** these outputs will provide an overall view of all data collected under emicizumab prophylaxis (including control arm patients after switch [Arm Cemi]) and will include analyses of safety and descriptive efficacy
- **Intra-patient comparisons:** for evaluations of the change in the number of treated bleeds and all bleeds over time compared with the patient’s historical bleed rate, only patients who participated in the NIS BH29768 are included

Of note, patients may be allowed to up-titrate their emicizumab dose as described in Section 2. The data under the new, higher dose are analyzed and reported separately. Additional summaries will be produced for key safety and exposure on all data (i.e., data before and after up-titration). Note, with longer follow-up or in case up-titration occurs more frequently than expected, outputs on all data may form the core analysis and additional summaries will be produced by dose.

### 4.2 **ANALYSIS POPULATIONS**

#### 4.2.1 **Randomized Population (ITT)**

The randomized population (intent-to-treat [ITT]) is defined as all randomized patients. The ITT population will be the primary analysis population for efficacy. Patients are analyzed according to their randomized treatment arm.

#### 4.2.2 **All Emicizumab Patients**

The All Emicizumab Patients population is the same as the randomized population for Arms A and B. For Arm C, only patients who switch to receive emicizumab are included.

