The number of bleeds can also be annualized for each patient using the following formula: $ABR = (\text{Number of bleeds during the efficacy period} / \text{Total number of days during the efficacy period}) \times 365.25$. If the NB model converges, van Elteren test to compare the mean ABR between the randomized arms will be provided only as a sensitivity analysis. However, if the convergence of the NB model is not achieved or is questionable, the primary efficacy analysis will be based on the van Elteren test of ABR.

For Arm D, one efficacy objective is to evaluate the clinical effect of prophylactic emicizumab on the number of bleeds over time. This analysis will be performed separately as well as overall as appropriate.

A detailed description of the statistical methods for the primary and secondary efficacy analyses will be provided in the SAP.

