6.5 SAFETY ANALYSES

The safety analyses population will be based on all enrolled patients grouped according to the actual treatment received. For Arm C patients, all safety data reported up to the day prior to switching will be included in the "control arm" safety summaries, and all safety data reported on or after the date of switching to active treatment will be reported separately.

Safety will be assessed for Arms A, B, and C and separately for Arm D through descriptive summaries of adverse events, laboratory test results (serum chemistry and hematology, including complete blood count with differential), ECGs, vital signs, and antibodies to emicizumab and FVIII.

To evaluate the overall safety of prophylactic emicizumab compared with no prophylaxis, the incidence of adverse events will be summarized and presented by System Organ Class mapped term, appropriate thesaurus level, and toxicity grade for each treatment arm.

For clinical laboratory data, summary statistics will be presented by treatment arm. In addition, shift tables describing changes from baseline will be presented using the WHO toxicity grading scale.

Data on the effect of immunogenicity (anti-emicizumab antibodies) on safety, efficacy, and/or clinical pharmacology and pharmacokinetics will be summarized adopting standard language/terminology (Shankar et al. 2014).

Although this is an open-label study, Sponsor personnel will not have access to safety summaries by treatment arm prior to the formal reporting of the study results. HCPs at participating study sites, as well as the Sponsor's drug safety and medical monitoring staff, will have access to the treatment assignments of patients for safety monitoring purposes only.

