#### **4.2.5 Safety Population**

Two safety analysis populations are defined below:

- Safety Population 1 (SAF1) includes all patients in Arms A and B who received at least one dose of emicizumab and patients in Arm C who started the study period, defined as having a Week 1 visit.
- Safety Population 2 (SAF2) is exactly the same as SAF1 for patients in Arms A and B. For patients in Arm C, SAF2 includes all patients who switched to emicizumab and received at least one dose of emicizumab.

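### SAP 4.2.2 lets never-dosed Arm A and B patients into the All Emicizumab Patients population, which can distort the descriptive mean ABR; separately, the SAP has no text for Arm D

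*SAP*

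**What the plan says.** SAP 4.1 sets out three output layouts. Of the second, for all emicizumab patients, it says "these outputs will provide an overall view of all data collected under emicizumab prophylaxis", and adds that the outputs "will include analyses of safety and descriptive efficacy".

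SAP 4.2.2 fills this layout by two different rules. For the arms randomized to the drug: "The All Emicizumab Patients population is the same as the randomized population for Arms A and B". SAP 4.2.1 gives the meaning of that reference: "The randomized population (intent-to-treat [ITT]) is defined as all randomized patients". For the control arm, 4.2.2 says: "For Arm C, only patients who switch to receive emicizumab are included".

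SAP 4.2.5 defines SAF2 on a dosed basis. Arms A and B follow SAF1, which requires at least one dose, and for the control arm: "For patients in Arm C, SAF2 includes all patients who switched to emicizumab and received at least one dose of emicizumab".

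SAP 2.3.1.1 keeps a patient who withdraws before the Week 1 visit and sets that patient's efficacy period to one day. Week 1 is when Arm A and B patients are expected to receive their first dose.

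None of these sections mentions Arm D. SAP section 2 describes a study in patients aged 12 or older in Arms A, B and C, and SAP Appendix 1 reproduces the synopsis of protocol Version 3. The current protocol is Version 5 and includes Arm D.

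**The concern.** A table presented as experience on emicizumab should contain people who took emicizumab. As written, Arms A and B enter by assignment and Arm C enters by treatment, side by side in one layout. A patient randomized to Arm A or B who leaves before the first dose is therefore shown as on-drug experience.

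The SAP foresees such patients and specifies how to count them, so this is a rule that will operate if the case arises. With a one-day period and no recorded bleed, the calculated ABR in SAP 4.5.1 is 0, the best possible value. What is at stake is the descriptive efficacy summary of bleed control on the drug, in particular the unweighted mean of the individual calculated ABRs.

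The second issue is coverage. Protocol 6.4.1 leaves the detailed efficacy methods to the SAP, and the SAP gives none for Arm D.

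**Working it through.** **The plan's own figure.** The only sample-size figure nearby is power above 90% (SAP 2.4). Using a Wald test on the log rate ratio with ABR 4 versus 18, variance 10 × mean on the annual scale, 0.5 years of follow-up and 28 versus 14 patients:

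- Dispersions, (variance − mean)/mean²: (40 − 4)/16 = 2.25 and (180 − 18)/324 = 0.50.
- Variance: (1/(4 × 0.5) + 2.25)/28 + (1/(18 × 0.5) + 0.50)/14 = 0.0982 + 0.0437 = 0.1419.
- z: ln(18/4)/√0.1419 − 1.96 = 3.99 − 1.96 = 2.03, so power is 97.9%.

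This agrees with the plan on that reading of the variance. The comparison uses the ITT population, so nothing below alters it.

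**Who enters, by set.**

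| Set | Arms A and B | Arm C |
|---|---|---|
| All Emicizumab Patients (4.2.2) | all randomized | switched to emicizumab |
| SAF2 (4.2.5) | at least one dose | switched and at least one dose |

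The difference in Arms A and B is exactly the patients who were randomized and never dosed.

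**How such a patient is scored.** The formula in SAP 4.5.1 is ABR = bleeds / days × 365.25. With 0 bleeds in 1 day, ABR = 0. Zero is the typical count for two reasons. SAP 2.2.1 hands out the bleed-recording device only at the Week 1 visit. And even at the plan's control ABR of 18, one day carries only 18/365.25 = 0.049 expected bleeds.

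**Effect on an arm.** Inputs: 28 patients per arm and ABR 4 (SAP 2.4), and 168 days (24 weeks) for each dosed patient. The documents give no count of undosed patients, so the range 0 to 3 is an assumption.

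- Mean calculated ABR with k undosed: 4 × (28 − k)/28.
- Time-weighted rate: 4 × 168(28 − k) / [168(28 − k) + k].

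| k | Mean calculated ABR | Change | Time-weighted rate |
|---|---|---|---|
| 0 | 4.00 | none | 4.000 |
| 1 | 3.86 | −3.6% | 3.999 |
| 2 | 3.71 | −7.1% | 3.998 |
| 3 | 3.57 | −10.7% | 3.997 |

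In a single column of all 70 patients (28 + 28 + 14, every Arm C patient switching), one undosed patient gives 4 × 69/70 = 3.94, a change of −1.4%.

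**The rarer case.** If a bleed were recorded on that single day, the patient's ABR would be 365.25 and the arm mean (27 × 4 + 365.25)/28 = 16.9. Requiring one dose removes either distortion.

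**Arm D, set side by side.** Protocol 6 says Arm D analyses are descriptive and performed separately. Protocol 6.5 opens with "The safety analyses population will be based on all enrolled patients grouped according to the actual treatment received" and goes on to assess Arm D separately from Arms A, B and C. Protocol 6.4.1 says of Arm D bleeds: "This analysis will be performed separately as well as overall as appropriate". Protocol 6.4.2 adds a descriptive quality-of-life analysis of patients aged 8 to 17 across all four arms. The SAP contains no counterpart to any of these.

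**The case against.** The strongest reply is that this is a wording gap with little numerical reach. Safety already has a dosed-only set in SAF2. Efficacy on an as-randomized basis and safety on an as-treated basis is what the protocol describes. The number of undosed patients is unknown, the time-weighted rate barely moves, and the formal testing hierarchy uses ITT.

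Most of that stands, and it limits the point to descriptive efficacy. It does not remove the mismatch. This layout is defined by treatment received, Arm C is handled that way, and the ITT outputs already supply the as-randomized view. Nor do SAP 4.1 or 4.7 say which population governs the safety outputs in this layout.

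Three stronger readings are tempting, and the documents do not support them:

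- A reader might infer that the safety tables count undosed patients. SAF2 requires a dose in every arm it covers, and nothing says 4.2.2 replaces it for safety.
- A reader might infer that 4.2.2 deliberately leaves out children. Ages 12 to 17 are eligible and form a subgroup in SAP 4.5.5, so only patients under 12 are absent. That absence comes from the SAP being written to protocol Version 3.
- A reader might infer that Arm D belongs in a pooled all-emicizumab safety total. Protocol 6 and 6.5 call for separate Arm D reporting. The phrase in Protocol 6.4.1 about an overall analysis is conditional and concerns bleeds only.

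**Conclusion.** The point holds for descriptive efficacy. SAP 4.2.2 has no dosing condition for Arms A and B. Together with the one-day rule, it would usually enter an undosed early leaver as an ABR of 0 in outputs described as experience on the drug. The size is about 3.6% off an arm's mean calculated ABR per such patient, in the drug's favour, and almost nothing on the time-weighted rate. The primary comparison and its power do not change.

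This rests on a true mean ABR of 4, 28 patients per arm, and undosed patients leaving before Week 1 with no recorded bleed. The documents do not show whether any such patient exists. A patient who attended Week 1 but was never dosed would fall outside the one-day rule and contribute untreated follow-up, which could push the mean the other way. That too argues for a dosing condition.

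The Arm D gap is real but separate. It is a misalignment between the SAP and the current protocol, affecting the 15 planned patients under 12.

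**What to change.** 1. Redefine SAP 4.2.2 as patients in Arms A, B and C who received at least one dose of emicizumab, with data counted from the first dose. This matches the Arm C rule, where the second efficacy period already starts at first dose.
2. State in SAP 4.1 or 4.7 that safety outputs in this layout use SAF2.
3. For Arm D, either add efficacy and safety populations reported descriptively and separately, as Protocol 6 and 6.5 require, or refer to a separate Arm D plan. Whichever is chosen should say how the cross-arm quality-of-life summary in Protocol 6.4.2 is handled and whether any overall bleed analysis is intended. A pooled total that includes Arm D should not be required.

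Items 1 and 2 cost a few lines of SAP text and a check of table denominators. Item 3 needs a short section or a cross-reference, with table shells if the section is added. None needs new data.

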#### **4.2.3 Non-Interventional Study (NIS) Population**

The NIS population includes all patients who participated in NIS BH29768 prior enrollment to this study. It consists of patients previously treated with episodic FVIII or bypassing agents.

#### **4.2.4 Pharmacokinetic-Evaluable Population**

The PK-Evaluable population includes all patients who have received at least one dose of emicizumab and have at least one post-baseline emicizumab concentration result.

#### **4.2.5 Safety Population**

Two safety analysis populations are defined below:

- Safety Population 1 (SAF1) includes all patients in Arms A and B who received at least one dose of emicizumab and patients in Arm C who started the study period, defined as having a Week 1 visit.
- Safety Population 2 (SAF2) is exactly the same as SAF1 for patients in Arms A and B. For patients in Arm C, SAF2 includes all patients who switched to emicizumab and received at least one dose of emicizumab.

#### **4.2.6 Up-titrated Population**

The Up-Titrated population (UPT) includes patients whose emicizumab dose was up-titrated to 3 mg/kg/wk.

### **4.3 ANALYSIS OF STUDY CONDUCT**

Flow of patients through the study will be displayed in a “CONSORT” diagram. A clear account of all patients who entered the study, who were enrolled and randomized, and who entered and completed each phase of the study will be displayed. In addition, reasons for premature discontinuations from study treatment and reasons for withdrawing from the study (e.g., during follow-up) will be described.

Major protocol deviations will be summarized.

Observation time and duration of follow-up, as well as adherence to planned scheduled assessments and compliance with data entry into the electronic handheld device will also be evaluated.

### **4.4 ANALYSIS OF TREATMENT GROUP COMPARABILITY**

Comparisons between the treatment arms of demographic data (e.g. age, sex, race/ethnicity, weight, and height) and baseline disease characteristics (e.g., number of bleeds in the past 24 weeks, previous hemophilia treatments, and number of target joints) will be conducted to establish if any observed differences between the treatment arms are not due to imbalances in patient characteristics at baseline. Only descriptive analyses are planned, and no formal statistical tests will be applied.

## 4.5 EFFICACY ANALYSIS

The primary and secondary efficacy analyses will be based on the randomized population (see Section 4.2.1). Subgroup analyses by inhibitor status will be performed for primary and selected efficacy endpoints. Detail will be described in Data Analysis Plan.

### 4.5.1 Primary Efficacy Endpoint

The primary efficacy objective is to evaluate the clinical effect of prophylactic emicizumab compared with no prophylaxis on the number of bleeds over time. The definition of a bleed is described in Section 2.3.1. The primary endpoint is based on treated bleeds.

The comparison of the number of bleeds over time between the randomized treatment arms will be performed using an NB regression model, which accounts for different follow-up times, with the patient's number of bleeds as a function of randomization and the time that each patient stays in the study (the length of the efficacy period) included as an offset in the model. The model also includes the number of bleeds ( $<9$  or  $\geq 9$  according to the eCRF data) in the last 24 weeks prior to study entry as a stratification factor. This analytic model estimates the rate ratio,  $\lambda_t/\lambda_c$ , which quantifies the risk of bleeding associated with prophylactic emicizumab ( $\lambda_t$ ) in comparison to no prophylaxis ( $\lambda_c$ ). Statistical significance is controlled at the 2-sided, 0.05 alpha ( $\alpha$ ) level.

Of note, hierarchical testing is used to account for multiple testing and the first test to be included in the hierarchy is the emicizumab 1.5 mg/kg/wk maintenance dose versus control. The second test will be 6 mg/kg/4wks maintenance dose versus control. A global approach using a model statement (within GENMOD) with a 3-level categorical effect for treatment ("1.5 mg/kg/wk," "6 mg/kg/4wks," or "no prophylaxis") and an appropriate contrast statement will allow both tests to be performed via the following hypothesis

$H_0$  (null hypothesis): Rate Ratio = 1 versus  $H_1$  (alternative hypothesis): Rate Ratio  $\neq 1$ .

Statistical significance at the prespecified  $\alpha$  level will be based on a Wald testing procedure. Bleed rates for prophylactic emicizumab and no prophylaxis and the rate ratio will be presented and include 95% CIs.

The number of bleeds can also be annualized for each patient using the following formula:

$$ABR = (\text{Number of bleeds} / \text{Total number of days during the efficacy period}) \times 365.25.$$

Both the model-based method (estimated ABR from the NB model) and the method using the above formula (calculated ABR) will be used to describe the study results.

If the NB model converges, the Van Elteren test to compare the mean ABR between the randomized arms will be provided as a sensitivity analysis. However, if the convergence of the NB model is not achieved or is questionable or no bleeds at all were observed in one of the treatment arms, the primary efficacy analysis will be based on the Van Elteren test of ABR, according to the above formula.

Of note, the Van Elteren test will be applied separately for the Arm A versus Arm Ccontrol (using only patients randomized to Arms A and Ccontrol) and for the Arm B versus Arm Ccontrol comparisons.

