3.3 RATIONALE FOR STUDY DESIGN

This is a multicenter, open-label, Phase III clinical study with randomized and non-randomized arms. Patients aged 12 years or older with hemophilia A with or without inhibitors against FVIII will be randomized to receive one of the following regimens:

- Emicizumab prophylaxis at 3 mg/kg QW for 4 weeks, followed by 1.5 mg/kg QW subcutaneously (Arm A)
- Emicizumab prophylaxis at 3 mg/kg QW for 4 weeks, followed by 6 mg/kg Q4W subcutaneously (Arm B)
- No prophylaxis control arm (Arm C)

Patients aged <12 years with hemophilia A with inhibitors against FVIII will be enrolled to receive the following regimen:

- Emicizumab prophylaxis at 3 mg/kg QW for 4 weeks, followed by 1.5 mg/kg QW subcutaneously (Arm D)

This prospective, randomized design (Arms A, B, and C) allows uniform collection of bleed data, medication use, and patient-reported outcomes (PROs) through the use of patient-validated measurement tools in all groups, enabling analysis of the effect of prophylactic emicizumab versus episodic therapy on these important measures.

Reporting of bleeds by patients to their providers (e.g., doctors, nurses) is not standardized and can be incomplete in routine clinical care. In addition, the recording of bleeds by providers in medical records may be inconsistent. Therefore, testing the primary endpoint using a prospective randomized design is superior to comparison to historical control in patients who were not on prophylaxis prior to enrollment.

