3.3.3 Rationale for Control Group

The control group for the primary efficacy endpoint will be a concurrent, no prophylaxis "usual care" arm, in which patients who were on episodic therapy prior to study entry will be randomized (2:2:1 prophylactic emicizumab 1.5 mg/kg QW:prophylactic emicizumab 6 mg/kg Q4W:no prophylaxis), which will enable an inter-patient comparison of the treatment and control groups.

A second comparison will be a comparison to an individual patient's bleed rate calculated over the 24 weeks prior to study entry, from the medical record. This will enable intrapatient analyses of bleed rates to be performed.

All patients, whether assigned to receive prophylactic emicizumab or no prophylaxis, will continue to receive FVIII or rFVIIa on an episodic basis for the treatment of breakthrough bleeds during the study. Specific doses of FVIII or rFVIIa will not be mandated in the study but investigators should review with patients and approve the appropriate dose to be used to treat breakthrough bleeds. For patients receiving emicizumab, breakthrough bleeds should be treated with the lowest FVIII or rFVIIa dose expected to achieve hemostasis, which may be lower than the patients' prior FVIII or rFVIIa dose.

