4.5.2 Medical History and Demographic Data

Medical history includes clinically significant diseases, procedures, abuse of alcohol and drugs within the past year, and medication allergies. In particular, sites should record whether the patient has any history of prior immune tolerance induction, anaphylaxis, or known thrombophilia. It should also include all medications taken within the 4 weeks prior to screening (including prescription, over-the-counter, and herbal/homeopathic remedies and therapies), or in the 24 weeks prior to screening for medications intended to treat osteopenia or osteoporosis. If the interval between screening and Week 1 is

longer than 2 weeks, all medications taken during this period should be reviewed and recorded. If imaging tests of bone health (e.g., densitometry, dual energy X-ray absorptiometry [DEXA] scan) were performed in the year prior to screening, the results should be recorded.

Additionally, the number of bleeds during the 24 weeks prior to study enrollment should be documented, as well as the number of school/work days missed and number of days hospitalized during the 24 weeks prior to study entry.

Demographic data will include age, sex, and self-reported race and ethnicity.

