## **2. STUDY DESIGN**

[figure not shown]
Study YO39309 is a randomized, multicenter, open-label, Phase III clinical study will enroll patients aged 12 years or older with hemophilia A regardless of FVIII inhibitor status. Approximately 70 patients who received episodic treatment with FVIII or bypassing agents prior to study entry and experience at least 5 bleeds over the prior 24 weeks will be randomized in a 2:2:1 ratio to the following regimens:

- Arm A: Emicizumab prophylaxis at 3 mg/kg QW subcutaneously for 4 weeks, followed by 1.5 mg/kg QW subcutaneously
- Arm B: Emicizumab prophylaxis at 3 mg/kg QW subcutaneously for 4 weeks, followed by 6 mg/kg Q4W subcutaneously
- Arm C: No prophylaxis (control arm)

Randomization will be stratified according to the number of bleeds patients experienced over the last 24 weeks prior to study entry, <9 versus  $\geq 9$  (or ABR 18), to ensure a balance of patients with lower versus higher number of bleeds in all arms. All patients will continue usual episodic treatment with FVIII or bypassing agents in case of a breakthrough bleeding event.

To ensure a representative variety of patients with hemophilia A enrolled in this study to investigate the efficacy and safety profile of emicizumab in both inhibitor and non-inhibitor populations, enrollment of up to 55 non-inhibitor patients will be permitted. Study patients will be enrolled globally from China and other Asia Pacific countries. At least 60 patients will be enrolled from China and Hong Kong. The study schema is shown [Figure 1](#).

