### **4.5.2.3 Treated Joint Bleeds**

The definition of treated joint bleeds is described in Section 2.3.2.3. The analysis methodology is the NB regression model or the Van Elteren test, the same as for the primary endpoint.

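### The bleed models adjust for prior bleeding only as below 9 versus 9 or more, although the full count is recorded; this may lose some precision

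*SAP*

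**What the plan says.** SAP 4.5.1 fits an NB model with a three-level treatment term, the length of the efficacy period as offset, and the number of bleeds (two levels, cut at 9, from eCRF data) "in the last 24 weeks prior to study entry as a stratification factor". This matches the allocation in SAP 3.1: "A block based randomization method will be used, stratified by the number of bleeds in the last 24 weeks", with the same cut.

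The secondary bleed endpoints inherit the model. For treated joint bleeds, SAP 4.5.2.3 states: "The analysis methodology is the NB regression model or the Van Elteren test, the same as for the primary endpoint". All bleeds, treated spontaneous bleeds and treated target joint bleeds are handled in the same way.

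The count itself is available. Eligibility requires bleeds to be documented over at least 24 weeks (Protocol 4.1.1.1), and Protocol 4.5.2 says that "the number of bleeds during the 24 weeks prior to study enrollment should be documented". SAP 4.4 lists "number of bleeds in the past 24 weeks, previous hemophilia treatments, and number of target joints" among the baseline characteristics, for descriptive comparison only. No bleed-rate model is stated to use the full count. The sensitivity list in SAP 4.5.4 names an ANCOVA but gives no covariates.

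**The concern.** SAP 3.1 itself treats prior bleeding as prognostic. Patients must "experience at least 5 bleeds over the prior 24 weeks", and there is no upper limit, so the upper stratum is open-ended. A patient with 9 prior bleeds and one with 40 get the same adjustment, while patients with 8 and 9 get different ones. Stratified blocks balance the split but not the counts inside it, and the control arm is planned at 14 patients. The cut is also not applied consistently: the subgroups in SAP 4.5.5 are 9 or fewer versus more than 9, so a patient with exactly 9 bleeds changes group.

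If prior and on-study bleeding are closely related, a continuous term would absorb between-patient variation that the split leaves in the dispersion, and would adjust for chance imbalance within a stratum. Under the log-link model, the treatment effect is still a rate ratio after the covariate is added. At stake are the width of the intervals and the six secondary bleed tests in the hierarchy of SAP 4.5.2, for which no power is stated.

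**Working it through.** **The plan's own power.** Inputs from SAP 2.4: ABR 4 and 18, variance 10 × mean, 28 and 14 patients per comparison, 0.5 years, two-sided 0.05. Setting mean + k·mean² = 10·mean gives k = 9/mean, so k = 2.25 on emicizumab and 0.5 in controls.

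- Variance of log RR = (1/(4 × 0.5) + 2.25)/28 + (1/(18 × 0.5) + 0.5)/14 = 0.0982 + 0.0437 = 0.1419; SE = 0.377.
- |ln(4/18)|/SE = 1.504/0.377 = 3.99; power = Φ(3.99 − 1.96) = 97.9%.

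This agrees with the stated figure of more than 90%. If the variance rule is read on the 24-week scale (means 2 and 9, k = 4.5 and 1), the variance is 5.0/28 + 1.111/14 = 0.258, the SE 0.508 and the power 84%. The annual reading is therefore the one that fits.

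**Adding log(prior count) to the split.** The documents give no correlation between a patient's underlying bleeding tendency before entry and on study, so it was varied. Three sets of simulated trials (28/28/14) compared the model with both terms against the split alone:

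- Set 1: 3,000 trials per setting from 0.3 to 0.7, stratified blocks of 5; prior counts NB with mean 8 and k 0.5, truncated at 5 or more (median 9, 57% at 9 or more). The zero-correlation run used simple allocation.
- Set 2: 12,000 stratified trials per setting, prior dispersion 0.5, correlation on emicizumab half that in controls.
- Set 3: 3,000 trials per setting, stratified blocks, indexed by the control-arm correlation.

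Change in the empirical variance of the log rate ratio:

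| Correlation | Set 1, plan's k | Set 1, common k = 1 | Set 2 | Set 3 |
|---|---|---|---|---|
| 0 | about +4% | – | +0.8% | +0.2 to +0.5% |
| 0.3 | +1.3% | +2.5% | +0.8% | – |
| 0.5 | +1.8% | −0.5% | −1.6% | −2 to −6% |
| 0.7 | −3.0% | −8.4% | −3.4% | −5 to −12% |
| 0.9 | – | – | – | −12 to −22% |

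Simulation error in set 1 is about 2–3% on each SE, although the models were fitted to the same simulated data; differences of 1–2% should not be over-read. Model-based variances in set 1 fell further (2.2%, 6.0% and 14.0% at 0.3, 0.5 and 0.7). At 0.7, however, the model-based SE (0.355) was below the empirical one (0.369), so the empirical column is the safer guide. On the 24-week reading, which does not fit the plan's power, simple-allocation runs showed a cost of 5.4% at 0.3 and 1.7% at 0.5.

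**Effect on the primary test.** In set 1 with the plan's k, power moved from 97.8% to 98.4%, 98.4% to 98.9% and 99.4% to 99.8% at 0.3, 0.5 and 0.7.

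**Endpoints with fewer events.** In the formula above, the Poisson part is 0.5/28 + 0.1111/14 = 0.0258, or 18% of 0.1419. With rates cut to one-third (an assumption) and k unchanged, it is 1.5/28 + 0.3333/14 = 0.0774 out of 0.0774 + 0.1161 = 0.1935, or 40%. No baseline covariate removes that part. In set 2, the gain shrank from 3.4% to 0.8% at 0.7 and from 1.6% to 0.5% at 0.5.

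**The case against.** The planned model is a proper one. It adjusts for the factor used in randomisation, as Protocol 6.4.1 specifies, and the NB dispersion carries the remaining between-patient variation. The benefit of a continuous term depends on a correlation that nobody has stated, and at moderate values it may be nil or slightly negative.

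The covariate is also imperfect. Protocol 3.3.3 describes a "bleed rate calculated over the 24 weeks prior to study entry, from the medical record", and Protocol 3.3 concedes that "the recording of bleeds by providers in medical records may be inconsistent". The outcome is measured differently: device-recorded, treated, non-procedural bleeds under a 72-hour rule. A two-level split is less exposed to a few wrong high counts than a slope is. With 5% of counts misrecorded fourfold at correlation 0.5, the model with both terms cost 1.8% in variance, while log count in place of the split gained about 1%.

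All of this stands as a limit on size, and it rules out calling the change free. It does not remove the point: the split is derived from the same medical-record count, and an error across 8 and 9 moves a patient's whole adjustment. In two of the three simulation sets the cost at zero correlation was under 1%.

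A reader might also infer that the joint and spontaneous tests would gain most, because their power is unstated. The documents do not support this. Those endpoints are subsets of treated bleeds, so more of their variance is Poisson noise, and the recorded prior count is of bleeds overall, which may predict them less well.

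**Conclusion.** The point holds as an efficiency improvement. The full count is collected and the bleed models use only a split at 9, so some precision may be lost and imbalance within strata goes unadjusted. The gain is roughly nil at correlations of 0 to 0.3, uncertain in sign at 0.5, about 3–12% of variance at 0.7, and larger only above that. These figures rest on assumed correlations, assumed prior-count distributions and, outside the misrecording check, error-free counts.

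A reader might infer that the split is an analysis error, or that it wastes the equivalent of 10 or more patients. Neither follows. Including the stratification factor is correct, and primary power of about 98% leaves the main conclusion little to gain. Figures of 10 to 13 patients come from variance ratios of 0.880 and 0.839 (70 × (1/0.880 − 1) ≈ 10; 70 × (1/0.839 − 1) ≈ 13). Those ratios need a correlation of 0.9 in controls and 0.5–0.7 on emicizumab, which nothing in the documents establishes.

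**What to change.** Before any treatment-arm results are seen, add log(number of bleeds in the 24 weeks before entry) as a continuous covariate to the NB model in SAP 4.5.1, and so to 4.5.2.1–4.5.2.3. Keep the below-9 versus 9-or-more factor, and leave the Van Elteren strata as they are. The functional form must be fixed in advance.

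At a minimum, list this as an NB sensitivity model in SAP 4.5.4 for the primary and hierarchical bleed endpoints, with the stratified model kept as primary. It would show whether the rate ratios withstand adjustment for imbalance within strata, which no listed analysis clearly does. If arm-level results are already known, only this option remains, labelled as a later addition.

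The cost is one line in the model statement, one degree of freedom, reliance on medical-record counts and, if the correlation is weak, a small loss of precision. No new data are needed.
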